### **eGFR (CKD-EPI)cr slope of change from baseline**

Slope in change from baseline of eGFR (CKD-EPI)cr will be analysed by a random coefficient model allowing for random intercept and random slope per patient. The model will include the factors treatment, sex, geographical region, baseline LVEF, and status of DM as fixed effects and eGFR (CKD-EPI)cr at baseline (continuous), age (continuous), time and interaction of treatment by time and interaction of eGFR (CKD-EPI)cr at baseline (continuous) by time as linear covariates and allow for randomly varying slope and intercept between patients. The model will include all on-treatment change from baseline data.

Since the slope is run on the change from baseline data, the intercept will model the acute drop, whereas the long-term effect is modelled by the slope.

A plot of individual patient slopes and separately of individual patient intercepts will be provided per treatment and by eGFR at baseline.

Subgroup analyses as outlined in Section 6.4 will be explored for eGFR slope. The subgroup model will include additionally to the model described above, the subgroup if not already part of the model, subgroup by treatment and subgroup by treatment by time. If the subgroup variable is a categorization of a continuous covariate, this covariate will be dropped from the subgroup model.

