7.3.2 Secondary endpoint analyses

The key secondary endpoint occurrence of adjudicated HHF (first and recurrent) will be modelled using a joint frailty model together with adjudicated CV death in order to take into account the dependence between the endpoints. The joint frailty model will be adjusted for the same covariates as the primary analysis.

The joint frailty model therefore models the hazards in the following way:

$$r_i(t | \omega_i, Z_i) = \omega_i \exp \{ \beta'_1 Z_i \} r_0(t)$$

$$\lambda_i(t | \omega_i, Z_i) = \omega_i^\alpha \exp \{ \beta'_2 Z_i \} \lambda_0(t)$$

where $r_i(t)$ is the hazard of the recurrent HHF for the i th patient, proportional to the baseline intensity function r_0 . The hazard function of CV death for the i th patient is λ_i proportional to the baseline hazard λ_0 . β_1 and β_2 are vectors of the regression coefficients of the covariate vectors Z_i including treatment, age (continuous), gender, history of DM, geographical region, LVEF (continuous) and eGFR (CKD-EPI)_{cr} at baseline (continuous). Patient specific independent random effects are denoted by ω_i , with α giving the relation between HHF and CV death. Patient specific independent random effects denoted by ω_i and are assumed to follow a gamma distribution with mean 1.

The resulting likelihood function can be solved assuming piecewise constant hazards.

Slope in change from baseline of eGFR (CKD-EPI)_{cr} will be analysed by a random coefficient model allowing for random intercept and random slope per patient. The model will include the factors treatment, gender, geographical region, baseline LVEF, and status of DM as fixed effects and eGFR (CKD-EPI)_{cr} at baseline (continuous), age (continuous), time, interaction of treatment by time, and interaction of eGFR (CKD-EPI)_{cr} at baseline (continuous) by time as linear covariates and allow for randomly varying slope and intercept between patients. The model will include all on-treatment change from baseline data.

Since the slope is run on the change from baseline data, the intercept will model the acute drop, whereas the long-term effect is modelled by the slope.

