Rationale for change		
The inclusion criterion has different NTproBNP thresholds depending on presence or absence of atrial fibrillation and LVEF category. This inclusion criterion stipulates that the relationship between LVEF and outcome events is non-monotonic.
 
Implemented with this amendment to ensure consistency between TSAP and CTP.

Section to be changed		7.3.2 Secondary endpoint analyses
Description of change		The model will include the factors treatment, gender, geographical region, and status of DM as fixed effects and eGFR (CKD-EPI) _{cr} at baseline (continuous), LVEF (continuous), age

	
(continuous), time and interaction of treatment by time as linear covariates and allow for randomly varying slope and intercept between patients.
 
Was changed to:
 
The model will include the factors treatment, gender, geographical region, baseline LVEF and status of DM as fixed effects and eGFR (CKD-EPI)_{cr} at baseline (continuous), age (continuous), time, and interaction of treatment by time, and interaction of eGFR (CKD-EPI)_{cr} at baseline (continuous) by time as linear covariates and allow for randomly varying slope and intercept between patients.

Rationale for change
	
Implemented to allow for slope varying with baseline eGFR since this is a medically more reasonable model.
 
Implemented with this amendment to ensure consistency between TSAP and CTP.

Section to be changed
	
7.3.2 Secondary endpoint analyses
 
7.3.3 Further endpoint analyses

Description of change
	
7.3.2 Secondary endpoint analyses
 
Change from baseline in clinical summary score for HF symptoms and physical limitations domains of the KCCQ at week 52 will be evaluated by a mixed model for repeated measures data including baseline score, LVEF (continuous), age (continuous) and eGFR (CKD-EPI)_{cr} at baseline (continuous) as linear covariates and treatment, visit, baseline score by visit, visit by treatment, gender, geographical region and status of DM at baseline as fixed effects.
 
Was changed to:
 
Change from baseline in clinical summary score for HF symptoms and physical limitations domains of the KCCQ at week 52 will be evaluated by a mixed model for repeated measures data including baseline score, age (continuous) and eGFR (CKD-

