The tests will be performed in the following hierarchical order:

1. Time to first event of adjudicated CV death or adjudicated HHF
2. Occurrence of adjudicated HHF (first and recurrent)
3. eGFR (CKD-EPI)cr slope of change from baseline

Starting from step 1, if the null hypothesis of no difference is rejected, and the result is more favourable for empagliflozin, superiority is concluded in the tested endpoint, and the overall type I error is preserved for the test in the next step. If at any step the null hypothesis of no difference is not rejected, subsequent tests are conducted in an exploratory manner.

The overall type I error rate will be preserved at a level of 0.05 (2-sided). The type I error rate used at the final analysis will be influenced by the pre-planned interim analysis.

In the final analysis after the evaluation of recurrent HHF, alpha will be split into 0.001 to be used for the analysis of eGFR slope, and the rest will be transferred to the meta-analyses.

In case the trial is finished early at the time of interim analysis, using  $\alpha_{\text{interim}}$  for the primary and key secondary endpoints in the testing hierarchy according to the  $\alpha$ -spending function above, the following  $\alpha$ -split will be used for the eGFR slope analysis and the meta-analysis:

0.1 \*  $\alpha_{\text{interim}}$  will be used for the eGFR slope analysis and

0.9 \*  $\alpha_{\text{interim}}$  will be transferred to the meta-analyses

In both the interim and final analyses, if the slope analysis is successful, the alpha of this branch will then be transferred to the meta-analyses.

The testing hierarchy is summarized in Figure 7.4.1: 1.

[figure not shown]

Figure 7.4.1: 1 Hierarchical analysis of trial in HFpEF (1245.110) and the parallel trial in HFrEF (1245.121) showing the alpha-spending at the final analysis

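### In the confirmatory eGFR slope model, sex, region, LVEF, diabetes status and age adjust only the intercept and not the tested slope, which gives up a little precision at a very small alpha

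*SAP*

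**What the plan says.** SAP 7.5.1.1 and protocol 7.3.2 give the same random intercept and slope model for change from baseline in eGFR. The SAP states "The model will include the factors treatment, sex, geographical region, baseline LVEF, and status of DM as fixed effects"; the protocol has "The model will include the factors treatment, gender, geographical region, baseline LVEF, and status of DM as fixed effects". Baseline eGFR and age enter as linear covariates. The terms involving time are "time and interaction of treatment by time and interaction of eGFR" at baseline by time, and no others. SAP section 4 makes LVEF a three-level category in all models.

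The SAP also states what each part of the model is for: "the intercept will model the acute drop, whereas the long-term effect is modelled by the slope". On the data it says "The model will include all on-treatment change from baseline data".

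Baseline eGFR by time came in with Global Amendment 3 (protocol 11.3), for this reason: "Implemented to allow for slope varying with baseline eGFR since this is a medically more reasonable model". The amendment does not discuss the other covariates.

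The slope is third in the hierarchy. At the final analysis "alpha will be split into 0.001 to be used for the analysis of eGFR slope" (SAP 7.4.1). The same section gives it 0.1 times the interim alpha "In case the trial is finished early at the time of interim analysis". Randomisation is stratified by region, diabetes status and screening eGFR (protocol 7.6).

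**The concern.** The hypothesis is tested on the treatment-by-time coefficient. A covariate that enters only as a main effect moves a patient's whole line up or down. It explains none of the differences between patients in rate of decline, and those differences are part of what sets the standard error of the tested coefficient. Five listed covariates, two of them randomisation factors, therefore adjust the acute drop and leave the long-term slope unadjusted.

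Two things could be lost. One is precision, in a confirmatory test with a critical value above 3.2 whose alpha passes to the meta-analyses if it succeeds. The other is some robustness: only on-treatment data are used, and if the arms lose different kinds of patients from treatment, a slope mean that ignores those patient characteristics can be pulled differently in each arm.

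**Working it through.** **Alpha available.** The SAP's spending function at 60% information gives 0.025 × (1 − e^4.8)/(1 − e^8) = 0.00101 one-sided, which reproduces the stated 0.001. That is about 0.002 two-sided, so after an early stop the slope has about 0.1 × 0.002 = 0.0002 two-sided. Critical values are 3.29 at 0.001 and 3.72 at 0.0002. Both levels are read as two-sided because SAP 7.4.1 specifies two-sided tests.

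**No slope power figure exists to reproduce.** Protocol 7.7 and SAP 9.6 power the primary endpoint only. No slope SD, residual SD, target difference or slope power is given, so everything below rests on assumed values.

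**Main effects do not sharpen the slope.** With complete data on a common visit schedule, a patient's estimated slope has variance σ_b² + σ_e²/S, where σ_b is the between-patient slope SD, σ_e the residual SD and S the sum of squared deviations of the visit times.
- Visits at weeks 4, 12, 32, 52, 76 and 100 (protocol flow chart) have mean 46 and squared deviations summing to 6968 weeks². S = 6968/52² = 2.577 years².
- Assume σ_b = 3 mL/min/1.73 m² per year and σ_e = 6 mL/min/1.73 m². The variance is 9 + 36/2.577 = 22.97.
- It stays at 22.97 whether the main effects explain 0% or 20% of the intercept variance.
- If covariate-by-time terms explain a share R² of the slope variance, it becomes 22.97 − 9R². That is 22.52 (−2.0%) at R² = 5% and 22.07 (−3.9%) at R² = 10%.

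**Range of the gain.** The proportional fall is R² × σ_b²/(σ_b² + σ_e²/S). Over σ_b from 2 to 5 and σ_e from 5 to 9 the multiplier runs from 4/(4 + 81/2.577) = 0.113 to 25/(25 + 25/2.577) = 0.720. R² is beyond what baseline eGFR already explains.

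| Assumed R² | Fall in variance | 80% power at 0.001 becomes |
|---|---|---|
| 2% | 0.2–1.4% | 80.1–80.8% |
| 5% | 0.6–3.6% | 80.3–82.1% |
| 10% | 1.1–7.2% | 80.7–84.1% |

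With follow-up to week 52 only, the fall is at most 3.4% even at R² = 10%.

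**A simulation closer to the trial.** Assumptions: 3600 patients, visits from week 4 to 148, follow-up 0.5 to 3 years, 10% per year stopping drug, slope SD 4.5, residual SD 6.5, and a diabetes effect on slope of −0.5 to −1.5 per year. Adding time interactions for the listed covariates gave variance ratios of 0.998, 0.986 and 0.968 for smaller, base-case and larger covariate effects. Power is Φ((3.2905 + 0.8416)/√ratio − 3.2905), which gives 80.1%, 80.8% and 81.8%.

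**Dropout bias.** This is a large-sample calculation with one binary covariate at 50% prevalence, a slope difference of 0.5 to 2 per year between its levels, N = 3600, slope SD 3 and residual SD 6. The bias in the treatment slope difference, in mL/min/1.73 m² per year, when covariate by time is omitted is:
- stopping depends on the covariate equally in both arms: 0;
- additive arm effect on stopping: at most 0.0006;
- modest arm-by-covariate difference (34% v 23% stopped in one level): 0.015–0.06, or 0.09–0.35 standard errors;
- strong difference (56% v 23%): 0.05–0.21, or 0.3–1.1 standard errors.

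Adding the interaction removed the bias in each of these cases. In the simulation, when placebo stopping also depended on UACR, the bias went from −0.13 to only −0.10 with the listed covariates by time. The fix reaches only what is in the model.

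**The case against.** The best defence is that the model is valid as written and that interacting only the endpoint's own baseline with time is the plan's convention. The repeated-measures models likewise use baseline by visit and keep sex, region, LVEF and diabetes as main effects, and Global Amendment 3 shortened those models partly to avoid convergence problems. The gain is small and rests on assumed inputs. Part of any age and sex effect may already be carried by baseline eGFR, whose formula uses both. Supporting eGFR analyses exist: slope subgroup models, repeated-measures models with and without off-treatment data, and an analysis at post-treatment follow-up. All of this stands. None of those analyses, however, re-estimates the overall slope difference with covariates acting on slope, and SAP 7.5.1.1 lists no sensitivity analysis for it.

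A reader might infer more than the documents support:
- **That dropout bias is present.** It needs stopping that differs between arms by covariate, together with an effect of that covariate on slope. Nothing in the documents shows this. If steeper decliners stop more often on placebo, the bias understates the benefit.
- **That stopping related to diabetes breaks the missing-at-random assumption.** Diabetes status is in the model, so such stopping is at random given the covariates. The possible fault is a misspecified slope mean.
- **That the stratification is unused.** The eGFR stratum is carried into the slope by baseline eGFR by time; region and diabetes status are not.
- **That the sponsor has conceded the general argument.** The amendment's rationale concerns baseline eGFR only.
- **That baseline UACR should simply be added.** SAP 7.6 treats UACR as missing when urine albumin is below quantification, and the covariate imputation rule in SAP 6.6.1 covers only Cox and recurrent-event models. The patients with the lowest albumin would drop out of a confirmatory test.

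**Conclusion.** The point holds as a low-cost improvement and is not an error in the plan. Five covariates already in the confirmatory model, including two of the three randomisation factors, do not inform the parameter being tested.

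The likely gain is a fall of about 0.2 to 3% in the variance of the slope difference, or roughly 0.1 to 1.8 points of power from a nominal 80% at two-sided 0.001. This rests on assumed variances, covariate effects and starting power. It would be larger only if these covariates explained as much as about 10% of slope variance beyond baseline eGFR.

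Protection against bias is a conditional second benefit whose size and sign cannot be derived from the documents. It would not cover discontinuation that depends on unmeasured factors, or the restriction to on-treatment data.

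**What to change.** Before unblinding, add to the slope model in SAP 7.5.1.1 and protocol 7.3.2 the interactions with time of diabetes status (2 parameters), geographical region (4), age (1), sex (1) and LVEF category (2). That is 10 parameters in about 3600 planned patients, with no new data. Treatment by time stays the tested parameter. Do not add UACR to the confirmatory model unless a rule for patients with baseline albumin below quantification is written first.

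The cost is one sentence in each document, a slightly larger model, and a late change to a confirmatory analysis that must be dated before unblinding. If the sponsor will not change the confirmatory model at this stage, the minimum is to pre-specify the extended model as a sensitivity analysis of the slope.

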## **7.5.2 Other Secondary endpoints**

Other secondary endpoints are exploratory. No correction for multiple hypotheses testing will be made.

- *Composite renal endpoint: Time to first event of chronic dialysis or renal transplant or sustained\* reduction of  $\geq 40\%$  eGFR (CKD-EPI)cr or*
  - *(for patients with eGFR (CKD-EPI)cr  $\geq 30$  mL/min/1.73 m^2 at baseline): sustained eGFR  $< 15$  mL/min/1.73m^2*

- (for patients with  $eGFR (CKD-EPI)_{cr} < 30 \text{ mL/min/1.73 m}^2$  at baseline): sustained  $eGFR < 10 \text{ mL/min/1.73 m}^2$

\*An  $eGFR (CKD-EPI)_{cr}$  reduction is considered sustained, if it is determined by two or more consecutive post-baseline central laboratory measurements separated by at least 30 days (first to last of the consecutive  $eGFR$  values). If there is no additional measurement  $\geq 30$  days after the  $eGFR$  reduction is observed and the patient dies within 60 days of this measurement, then the  $eGFR$  reduction is also considered sustained.

Chronic dialysis is regarded as chronic if the frequency of dialysis is twice or more per week for at least 90 days.

- Time to first adjudicated HHF
- Time to adjudicated CV death
- Time to all-cause mortality
- Time to onset of DM in patients with baseline pre-DM

All time-to-event endpoints will be reported in days.

The same model and data frame as used in the primary analysis of primary endpoint will be applied to all these time-to-event endpoints. If the endpoint does not include any cause of death, a CIF plot with all-cause mortality as competing risk will be displayed; otherwise, a CIF plot with causes of death not included in the endpoint as competing risk will be displayed. For all-cause mortality a Kaplan-Meier plot will be displayed.

For time to first HHF and time to CV death, the analysis will be repeated based on investigator defined events.

- Change from baseline in clinical summary score (HF symptoms and physical limitations domains) of the Kansas City cardiomyopathy Questionnaire (KCCQ) at week 52

Change from baseline in clinical summary score for HF symptoms and physical limitations domains of the KCCQ at week 52 will be evaluated by a mixed model for repeated measures (MMRM) including age (continuous) and  $eGFR (CKD-EPI)_{cr}$  at baseline (continuous) as linear covariates and, baseline score by visit, visit by treatment, sex, geographical region, baseline LVEF, and status of diabetes at baseline as fixed effects. An additional factor of “week reachable” for the parameter in question, which for each patient is the theoretically reachable planned measurement based on the time of randomisation will adjust for the different planned study times.

All on-treatment data up to week 52 will be included and the analysis will be conducted on the treated set.

A sensitivity analysis will be conducted including data after discontinuation (OC-AD) on the randomized set.

An additional analysis will be performed for the Clinical Summary Score on OC-AD without imputing a worst score for patients who die.

- *Occurrence of all-cause hospitalisation (first and recurrent)*

A similar joint frailty model as well as negative binomial regression model as in the HHF will be analysed for all-cause hospitalization. Instead of CV death, all-cause mortality will be jointly modelled as the terminal events in the joint frailty model.

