7.7 DETERMINATION OF SAMPLE SIZE

For the sample size calculation, a yearly event rate in the placebo group of 15% is assumed (ref. Paradigm 12% event rate [[R16-1460](#)], Rales 18 % event rate [[P99-02524](#)], and Emphasis-HF 15% event rate [[R16-1459](#)]). In the CHARM – added trial [[R06-0956](#)] event rate was 16.5%. The trial is designed to achieve a power of 90% for a two sided test at level $\alpha = 0.05$.

The following table ([Table 7.7: 1](#)) presents the number of required events together with the number of to be randomised and treated patients assuming an accrual period of 18 months and a follow-up period of 20 months for different assumed true hazard ratios. However, the follow-up period is not fixed but the trial will continue until the necessary number of events is observed, which are confirmed by the adjudication committee.

The drop-out rate from the trial is assumed to be very low (< 1% per year) and is therefore not further considered for the determination of sample size.

Table 7.7: 1 Sample size calculation without considering interim analysis

Yearly event rate for HHF+CV Death (placebo)	Hazard ratio	Number of events for 90% power for HHF+CV Death	Number of patients for 18 months accrual and 20months follow up
15%/Year	0.70	330	1178
15%/Year	0.75	508	1764
15%/Year	0.80	841	2850
15%/Year	0.85	1591	5268
15%/Year	0.90	3786	12256

A hazard ratio of 0.8 was chosen as a conservative estimate based on the results of EMPA-REG OUTCOME” described in [Section 1.2.3](#)

Therefore, at least 841 confirmed primary events should be observed and at least 2850 patients should be randomised and treated in order to achieve a power of 90% assuming a true hazard ratio of 0.8.

Including interim analysis with Hwang-Shih-deCani alpha spending with $\gamma=8$ at 60% of information will decrease the power only slightly (>89.5%).

The blinded event rate and recruitment progress will be assessed during recruitment before any interim unblinding. If the accumulated data suggests a slower accrual of primary outcome events over calendar time than originally projected, then the number of randomised patients may be increased to a maximum of 4000 patients. Operationally, the recruitment period would be extended and could continue up to 6 months before the target number of events is expected to be achieved. The number of confirmed primary outcome events will not be affected by this consideration and will remain 841 events.

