## **7.6 FURTHER ENDPOINTS**

### Time to event endpoints

Further time to event endpoints will generally be analysed in a Cox proportional hazards model similar to the primary analysis on RS. If the endpoint does not include any cause of death, a CIF plot with all-cause mortality as competing risk will be displayed; otherwise, a CIF plot with causes of death not included in the endpoint as competing risk will be displayed.

If there are less than 14 patients with events, then only descriptive statistics will be presented.

Further time to event endpoints are the following:

- Time from first to second adjudicated HHF
- Time to first all-cause hospitalisation
- Time to new onset of atrial fibrillation
- Time to adjudicated MI (fatal or non-fatal)
- Time to adjudicated stroke (fatal or non-fatal)
- Time to adjudicated TIA
- Time to first event of all-cause mortality or all cause hospitalisation
- Time to first event of adjudicated CV death or adjudicated non-fatal MI
- Time to first event of adjudicated CV death or adjudicated non-fatal stroke
- Time to first event of adjudicated CV death, adjudicated non-fatal MI or adjudicated non-fatal stroke (3-point MACE)
- Time to progression to macro albuminuria (defined as UACR >300 mg/g) from baseline for patients with baseline UACR ≤ 300 mg/g

- Time to first new onset of sustained normo- or micro albuminuria (UACR  $\leq$  300 mg/g) in patients with macro albuminuria at baseline
- Time to first new onset of sustained normo albuminuria (UACR  $<$  30 mg/g) in patients with micro- or macro albuminuria at baseline
- Time to first event of composite renal endpoint or adjudicated CV death
- Time to first event of composite renal endpoint, adjudicated CV death or adjudicated HHF
- Time to first event of composite renal endpoint or all-cause mortality
- Time to achievement of NT-proBNP  $<$  1000 pg/mL
- Time to first acute kidney injury (based on the preferred term)
- Time to non-cardiovascular (non-CV) death (death cases not included in the definition of adjudicated CV death)
- Time to first investigator defined CV hospitalization

Composite renal endpoint defined as: *chronic dialysis or renal transplant or sustained\* reduction of  $\geq$ 40% eGFR (CKD-EPI)cr or*

- *(for patients with eGFR (CKD-EPI)cr  $\geq$ 30 mL/min/1.73 m^2 at baseline): sustained eGFR  $<$ 15 mL/min/1.73m^2*

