For an evaluation of follow-up after discontinuation of trial medication an additional summary of the NT-proBNP, FG, eGFR, UACR, creatinine and the KCCQ endpoints as above will be produced. This summary will include descriptive statistics for baseline, actual values and change from baseline to last on-treatment value and follow-up, and change from last on-treatment assessment to follow-up. The TS-FU patient set will be the basis for this summary, but only those patients with a valid baseline, last value on treatment and follow-up value will be included in all displays. Analyses will be repeated for patients with at least 52 weeks of cumulative exposure (excluding treatment gaps). FG analysis will also be conducted by DM status at baseline (3 categories).

Analyses of change from baseline to LVOT and FU on the TS-FU outlined above will be additionally modelled, separately for LVOT and FU. An analysis of covariance (ANCOVA) model including treatment group, sex, geographical region, baseline LVEF and status of diabetes at baseline as fixed effects and baseline eGFR (CKD-EPI)cr (continuous), age (continuous), and baseline of the endpoint (if not already included) as linear covariates will be used.

In addition to the ANCOVA models described above, descriptive statistics will be presented also for creatinine for the value at visit and change from baseline based on OC-AD on the randomised set and OC-OT on the treated set.

In addition to the analyses defined above, KCCQ clinical summary score, clinical symptoms and physical limitations domain will be analysed in two responder analyses (1) defining an increase of 5 points or more from baseline as improvement and (2) defining a reduction of 5 points or more as deterioration.

The frequency and percentage (relative to RS) of patients with improvement as well as the frequency and percentage of patients with deterioration will be described. Patients lost to follow-up or who withdrew consent prior week 52 as well as patients who died prior week 52 will be considered as having a deterioration (no improvement) in KCCQ.

Improvement and deterioration will be analysed in separate logistic regression models including treatment, age (continuous), eGFR (CKD-EPI)cr at baseline (continuous), region, sex, baseline LVEF (categorical), status of diabetes at baseline, and baseline value of the KCCQ domain analyzed.

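### The Cox models for onset of diabetes, albuminuria change and NT-proBNP below 1000 omit the marker's own baseline value, which attenuates the hazard ratio and costs power in these exploratory analyses

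*SAP*

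**What the plan says.** The primary Cox model (Protocol 7.3.1, SAP 7.4.1) contains treatment, age, sex, region, diabetes status, LVEF category and baseline eGFR.

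- **Onset of diabetes in pre-diabetic patients** is an other secondary endpoint. SAP 7.5.2: "The same model and data frame as used in the primary analysis of primary endpoint will be applied to all these time-to-event endpoints". Protocol 7.3.2 agrees.
- **Progression to UACR above 300 mg/g, sustained regression to 300 mg/g or below, sustained regression to below 30 mg/g, and NT-proBNP below 1000 pg/mL** are further endpoints. SAP 7.6: "Further time to event endpoints will generally be analysed in a Cox proportional hazards model similar to the primary analysis on RS". This is looser than Protocol 7.3.3, which prescribes the same model as the primary analysis. Neither text adds a covariate.
- **Patients already past the threshold** at baseline are removed from the risk set (SAP 6.8.3). How far the others start from it is not used.
- **Other models in the same SAP** do use the starting value. The ANCOVAs specify "baseline of the endpoint (if not already included) as linear covariates will be used". The MMRMs carry a baseline-by-visit term, and the KCCQ 5-point responder models include the baseline of the domain analysed (SAP 7.5.2, 7.6).

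**The concern.** Time to crossing a fixed value depends heavily on where the patient starts. NT-proBNP shows how wide the spread can be. Under Protocol 3.3.2, criterion 5, a patient with EF of 30% or less and no AF can enter from 600 pg/mL. A patient with EF 36% to 40%, AF and no recent heart-failure admission needs at least 5000. Among those at risk, some start just above 1000 and others need more than an 80% fall (1 − 1000/5000). LVEF category captures part of this; AF and the value itself are not in the model.

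In a Cox model, leaving out a strong predictor that is balanced by randomisation does not bias the test under the null. It does move the estimated hazard ratio towards 1, and the test loses power. At stake is the precision of one listed secondary endpoint and four further endpoints, although the baseline values are collected at Visits 1 and 2 (Protocol Flow Chart).

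**Working it through.** **1. The plan's own figure.** The only sizing in the documents is for the primary endpoint: hazard ratio 0.80, 90% power, two-sided 0.05, 841 events, 2850 patients (Protocol 7.7).

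- Events by Schoenfeld: 4 × (1.960 + 1.282)² / (ln 0.80)² = 845, against 841 stated.
- Patients: "a yearly event rate in the placebo group of 15% is assumed", so the placebo hazard is −ln 0.85. With 18 months' uniform accrual and 20 months' follow-up, the mean event probability is 0.2958, and 841 / 0.2958 = 2843, against 2850 stated.

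Both reproduce. Neither says anything about the threshold endpoints. The documents give no power target, event fraction or marker distribution for them, so every input below is an assumption.

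**2. Mechanism.** Generic Cox simulation with a normally distributed marker, treatment hazard ratio 0.80, marker hazard ratio 2.72 per SD, and 50% of patients with an event:

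- with the marker: hazard ratio 0.802, standard error 0.052
- without it: hazard ratio 0.842, standard error 0.052
- information loss = 1 − (ln 0.842 / ln 0.802)² = 39%

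The standard error does not change; the whole loss is attenuation. Over marker hazard ratios of 1.65 to 2.72 per SD and 10% to 70% of patients with an event, the loss runs from 3% to 49%. If the existing covariates already explain a quarter of the marker's variance, it runs from 2% to 42%. A noisier run at 4.5 per SD gave 30% to 68%. This grid shows direction and mechanism; it does not mimic the endpoints.

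**3. Size, first trajectory simulation.** Marker = patient mean + drift + visit noise, read at the flow-chart visits, follow-up 0.6 to 2.6 years, 80 to 150 trials per scenario. Relative efficiency (RE) is the squared ratio of mean z, adjusted over unadjusted. The loss from omission is 1 − 1/RE.

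| Endpoint | n | Assumed within-person SD | RE | Loss |
|---|---|---|---|---|
| Onset of diabetes | 1000 | 0.12 / 0.20 / 0.30 (% HbA1c) | 1.22 / 1.13 / 1.07 | 18% / 12% / 7% |
| UACR above 300 | 1600 | 0.5 / 0.8 (log) | 1.41 / 1.10 | 29% / 9% |
| NT-proBNP below 1000 | 1500 | 0.25 / 0.45 (log) | 1.48 / 1.24 | 32% / 19% |

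The range is about 7% to 32%.

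**4. Size, second trajectory simulation.** Built separately, with baseline restricted to the at-risk window, first crossing at scheduled visits and 20 to 38 months of follow-up.

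| Endpoint | Loss across scenarios |
|---|---|
| Onset of diabetes | 2% to 39% |
| UACR above 300 | 28% to 44% |
| Sustained UACR 300 or below | 17% to 32% |
| Sustained UACR below 30 | 18% to 35% |
| NT-proBNP below 1000 | 12% to 39% |

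For onset of diabetes, the hazard ratio went from 0.51 adjusted to 0.59 unadjusted in the worst scenario, and stayed at 0.75 in the mildest.

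**5. What a loss L means.** For a comparison with 90% power when adjusted, power without the marker is Φ((1.960 + 1.282) × √(1 − L) − 1.960). L = 2%, 7%, 32% and 44% give about 89%, 88%, 76% and 68%.

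**The case against.** **No confirmatory claim is touched.** SAP 7.5.2 calls the other secondary endpoints exploratory, and the UACR and NT-proBNP endpoints rank below them. A reader might infer inflated type I error or a biased comparison. Neither follows: the randomised comparison stays valid and only power is affected. This stands, and it limits the priority.

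**A uniform covariate list is defensible.** It is prespecified in Protocol 7.3.2 and 7.3.3, and adding the marker changes the target to a more conditional hazard ratio. True, but the plan already departs from uniformity in its continuous and responder models and gives no reason for treating these endpoints differently.

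**Baseline-adjusted analyses of the same markers exist.** SAP 7.6 plans MMRMs for HbA1c, log UACR and log NT-proBNP. They answer a different question and do not restore power to the crossing endpoints.

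**Baseline HbA1c may matter less than assumed.** Protocol 5.1.2 also counts diabetes diagnosed by the investigator, which weakens the link. This stands, and supports the low end for that endpoint.

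**The size is uncertain.** With 80 to 150 trials, a simulated power near 50% has a Monte Carlo standard error of 4 to 6 points, so no simulated power figures are relied on here. A reader might also take RE 1.48 to mean that 48% of the information is lost. It means a 48% gain from adjusting, which is a 32% loss from omitting.

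**Log UACR is not a free covariate.** SAP 7.6 sets UACR to missing when urine albumin is below quantification. SAP 6.8.3 keeps patients without a baseline value at risk, and SAP 6.6.1 would impute the overall median. Some of the patients furthest from 300 mg/g would then be placed mid-range. This objection is right, and the fix must deal with it.

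**Conclusion.** The omission is confirmed for onset of diabetes and for the four UACR and NT-proBNP threshold endpoints, and it is out of line with the plan's other models. It attenuates the hazard ratio and costs power. Under assumed distributions, the loss of information is about 7% to 32% in one simulation and about 2% to 44% in the other; for onset of diabetes it may be negligible. The documents support no single figure and no firm upper limit.

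Two wider readings should be resisted. The SAP 7.5.2 sentence does not condemn every endpoint it covers: the renal composite in the same list has baseline eGFR in its model. Of the endpoints discussed here, that sentence governs only onset of diabetes; the others rest on SAP 7.6 and Protocol 7.3.3.

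This is a cheap improvement of modest priority, not a flaw in the confirmatory analysis.

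**What to change.** Before unblinding, add the marker's own baseline (as defined in SAP 6.7) as a continuous covariate in SAP 7.5.2 and 7.6, and record the departure from Protocol 7.3.2 and 7.3.3 in SAP section 4:

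- onset of diabetes: baseline HbA1c, dropping the constant diabetes-status term
- NT-proBNP below 1000: log baseline NT-proBNP
- the three albuminuria endpoints: log baseline UACR. Where it is missing because urine albumin was below quantification, use a separate indicator or a lower-limit value, not the population median of SAP 6.6.1. This matters mainly for progression, because the regression endpoints need a measured, raised baseline.

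Keep the current model as a supportive analysis.

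The cost is a few lines of SAP text, one covariate per model and one rule for low UACR, all from data already collected. The price is a more conditional hazard ratio and a covariate list that no longer matches the primary model exactly.
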